visits. Participants who use cannabis by vaping but are willing to smoke cannabis at the study visits will be allowed to enroll. Exclusion criteria: (1) pregnancy, (2) greater than occasional illicit drug use other than cannabis will be excluded; those with weekly or less frequent substance use will be enrolled but will be require to provide a negative urine drug test (other than cannabis) at each of the two study visits, (3) request for substance use treatment, (4) current parole or probation, (5) history of significant violent behavior within 12 months, (6) current uncontrolled major Axis I psychopathology requiring medical intervention (e.g. active psychosis, suicide risk,), or suicide attempt and/or suicidal ideation within 12 months (7) significant uncontrolled medical illness (such as late stage or metastatic cancer or on active treatment for cancer; chronic pulmonary disease on ventilator or continuous oxygen therapy); uncontrolled hypertension BP>160/100), (8) active heart disease within 12 months, (9) history of dementia, (10) severe hand tremor, (11) poor English fluency. All participants will be consented and compensated for their effort as approved by the IRBs of each participating institution (see Human Subjects).

RECRUITMENT. Established MWCCS research infrastructure and clinical populations will be used for study recruitment. In order to meet recruitment targets, electronic health records will be used to prescreen for eligibility in clinical populations. We have obtained a waiver to access records for recruitment purposes. Potential participants will be contacted via phone to provide initial information about the study and screen for eligibility, followed by an in-person screening visit and initial consent. Written informed consent will then be obtained in person prior to study enrollment.

RANDOMIZATION AND BLINDING. Each participant will smoke both inactive (0.0%) and active (7.0%) cannabis; the order in which each cannabis strength is administered will be counterbalanced and double-blind. Participants will be told that the strength of cannabis that they will smoke in each session will vary.

RESEARCH VISITS AND STUDY PROCEDURES

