holder, and the exposed end pinched to cover the leaves. Cannabis is administered using a standardized cued-smoking procedure, which produces reliable increases in heart rate and plasma Δ^9 - THC. Participants will be instructed to 'light the cigarette' (30 sec), 'get ready' (5 sec), 'inhale' (5 sec), 'hold smoke in lungs' (10 sec) and 'exhale.' Participants will smoke 1 puff/minute in this manner, with a 40-sec interval between each puff until 50% of the cigarette has been smoked. Cigarettes are stored frozen in an airtight container and humidified at room temperature for 24 hours before use.

PROPOSED TIMELINE. Table 2 depicts the timeline for recruitment and testing. Recruitment in the first quarter of Year 1 will be lower to account for study planning and initiation. Each participant will complete two study visits (minimum 48 hours apart) for a total of 120 visits. In the final 2 quarters, we will complete data collection, final reliability checks and statistical analyses, write manuscripts, and submit an R01 application.

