7. DATA ANALYSIS

OVERVIEW AND APPROACH: To determine the acute effects of cannabis on balance, mobility, and cognition among older HIV+ and HIV- women.

OUTCOMES: Primary outcomes are functional reach and gait speed (Aim 1) and number of correct suppressions on the Sustained Attention to Response Task (SART) (Aim 2) under active and inactive cannabis

STATISTICAL ANALYSIS: Descriptive data analysis will identify erroneous values, outliers, distributional properties, and insufficient data dispersion for making analytic comparisons. As needed, transformations such as logarithmic or categorization will be applied to skewed continuous variables. The HIV+ and HIV-arms will be compared using t-tests/ANOVA, and/or rank tests for continuous and exact tests for binary baseline covariates to identify potential confounders and generalizability issues. Within our crossover design for the outcomes of both Aims 1 and 2 with each subject getting both active and inactive cannabis (after verifying distributions are not too skewed for normal approximation), we will use linear mixed effects models, which take account of correlations among measurements within the same subjects, to compare functional reach and gait speed (Aim 1) and number of correct suppressions on the Sustained Attention to Response Task (SART) (Aim 2) after inactive vs. active cannabis administration, and to evaluate whether HIV+ women have greater declines in gait speed and functional reach and attention than HIV- women, after administration of active vs. inactive cannabis (i.e. by fitting interaction terms). In these models the 15, 60, 105 and 150 minute measures with baseline from the same visit subtracted will be the outcome(s). Because peak marijuana effect is expected to occur on 15 to 60 minutes, for the

purpose of effect size estimation, averaged 15 and 60 minute results (with baseline subtracted) will be the primary outcome(s) and this analysis reduces to a two way ANOVA or equivalently two sample t-test of differences in differences. Other quantitative and descriptive approaches previously applied to these measures¹⁰⁴ including area under the curve and trajectories will be fit.

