POWER CALCULATIONS: Under the standard approach to power estimation of hypothesis testing at a two sided α =0.05 with β =0.2, this study even with only 60 subjects is powered to detect (active vs. inactive cannabis) effect sizes of at least 0.53 for functional reach and 0.63 for walking time, both of which are considered to be medium. The power here is greatly increased by repeated measures being taken pre and post administration with the outcome being the difference of averaged measures that from our normative data have correlations of ρ =0.82 an 0.87 for walking time and functional reach which reduces the variances of within subject difference to 0.27 σ 2 and 0.195 σ 2 respectively. We do not have similar normative data for power estimation of other outcomes. Some authors believe that in pilot studies that will be later confirmed 105-107 a higher α =0.25 is appropriate, in which case, the detectable effect sizes drop to 0.32 for reach and 0.38 for walking time which are considered close to small. Other criteria besides hypotheses testing that are satisfied by smaller sample sizes should be considered for pilot studies 107-109 with other authors finding 20-70 subjects adequate for estimating standard deviations 110-112 and effect sizes 112,113 of outcomes and identification of subject exclusion criteria for the main study.

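### The primary two-sample t-test of differences in differences cannot use the counterbalanced smoking order; a regression on HIV status and order costs almost nothing and is modestly better.

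*Combined protocol and SAP*

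**What the plan says.** Section 2 (Randomization and Blinding) states that "the order in which each cannabis strength is administered will be counterbalanced and double-blind". The timeline in the same section adds "Each participant will complete two study visits (minimum 48 hours apart) for a total of 120 visits". The design is therefore a two-period crossover in 30 HIV+ and 30 HIV- women.

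Section 7 (Statistical Analysis) subtracts the same-visit baseline from each post-smoking measure. It takes the mean of the 15- and 60-minute changes as primary, with effect size estimation as the stated purpose, and says "this analysis reduces to a two way ANOVA or equivalently two sample t-test of differences in differences". The linear mixed models in the same paragraph are described as handling within-woman correlation and fitting interaction terms. Section 7 names no order, visit, period or sequence term, and no other section adds one. The documents also do not say whether order is balanced separately within HIV+ and HIV- women.

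**The concern.** The design controls order, but the primary test ignores it. Baseline subtraction cancels an additive difference between visits. It does not cancel a different baseline-to-post change at the second visit. Such a difference is most plausible for a computer task with practice effects such as the SART, for which the power section has no normative data.

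If π is not zero, it enters the active-minus-inactive difference with one sign in women who smoke active first and the opposite sign in the others. Under balanced order this is extra noise. Under unequal order between the HIV groups it also shifts the HIV contrast, which is the question of both aims.

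The SD matters beyond this study. The sample size is justified partly by the estimation of standard deviations and effect sizes, and the timeline ends with plans to "write manuscripts, and submit an R01 application".

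**Working it through.** **Inputs (section 7, Power Calculations).** Correlations are 0.82 (walking time) and 0.87 (reach). The text says averaging "reduces the variances of within subject difference to 0.27"σ² for walking and 0.195σ² for reach. Detectable effects are "effect sizes of at least 0.53 for functional reach and 0.63 for walking time" at two-sided α = 0.05 and 80% power, and 0.38 (walking) and 0.32 (reach) at α = 0.25. Group sizes are 30 and 30.

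**Reproducing the plan.** The per-visit change (mean of two post measures minus baseline) has variance V = 1.5(1 − ρ)σ², which is 1.5 × 0.18 = 0.27σ² and 1.5 × 0.13 = 0.195σ², as stated. Treating the two visits' changes as independent, the difference in differences has variance 2V = 0.54σ² and 0.39σ².

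- α = 0.25, 80% power: (1.150 + 0.842) × √(2 × 0.54/30) = 0.378 and (1.150 + 0.842) × √(2 × 0.39/30) = 0.321. These match the plan's 0.38 and 0.32, so this is the plan's error variance for the HIV+ versus HIV- comparison.
- α = 0.05, 80% power: the same variances give 0.54 and 0.46 (noncentral t, 58 df), not 0.63 and 0.53. At the stated effects power is about 90%. This mismatch is a separate matter. Both pairs are used below, taken as HIV-by-drug effects.

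**How order enters.** Let the change at visit 2 exceed that at visit 1 by π. A woman's difference is then δ − π if active is first and δ + π if inactive is first. With 15/15 in each HIV group, the variance becomes 2V + π² and the SD is inflated by √((2V + π²)/2V) − 1. For walking at π = 0.3σ: √(0.63/0.54) − 1 = 8.0%. For reach: √(0.48/0.39) − 1 = 10.9%.

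The values of π are assumptions. The largest, 0.3σ, is 0.3/√0.27 = 0.58 (walking) or 0.3/√0.195 = 0.68 (reach) of the SD of the per-visit change, which is large.

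**Power, order 15/15, same π in both HIV groups** (100,000 simulated trials per cell; t-test / regression with order, %):

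| | π = 0.1σ | π = 0.2σ | π = 0.3σ |
|---|---|---|---|
| Walking, SD inflation | 0.9 | 3.6 | 8.0 |
| Walking, effect 0.63 | 90.0 / 90.3 | 89.1 / 90.5 | 87.4 / 90.5 |
| Walking, effect 0.54 | 79.5 / 80.1 | 77.8 / 79.9 | 75.1 / 80.1 |
| Reach, SD inflation | 1.3 | 5.0 | 10.9 |
| Reach, effect 0.53 | 89.5 / 89.9 | 87.8 / 89.8 | 85.2 / 89.7 |
| Reach, effect 0.46 | 79.1 / 79.8 | 77.2 / 80.2 | 73.0 / 79.9 |

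At π = 0.3σ the t-test's type I error is 3.5% (walking) and 3.0% (reach). With the order term it is 5.1% and 5.0%.

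**Unequal order between HIV groups.** The HIV contrast shifts by 2π times the difference in active-first share.

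- 16/14 versus 14/16: 2π × (16/30 − 14/30) = 0.13π, or 0.04σ at π = 0.3σ.
- 18/12 versus 12/18: 2π × (18/30 − 12/30) = 0.4π, or 0.04, 0.08 and 0.12σ. Type I error conditional on that split is 5.3%, 6.0% and 7.1% (walking) and 5.4%, 6.4% and 7.8% (reach). The order term returns it to 5.0–5.1%.

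**π different by HIV group** (0.3σ in HIV+, 0 in HIV-, order 15/15). The extra variance is (0.09 + 0)/2 = 0.045σ² with no term, 0.15² = 0.0225σ² with a common order term, and 0 with HIV-by-order. Power for the three analyses at the plan's effects is 89.0, 89.7 and 90.4% (walking) and 87.5, 88.6 and 89.7% (reach). If order is also 20/10 in HIV+ and 15/15 in HIV-, the shift is 0.100σ, 0.053σ and 0.000σ respectively.

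**The case against.** The strongest reply is that nothing here is wrong. With balanced order the estimate is unbiased and the test conservative, and the size of any gain rests on a π that the documents do not give. No passage suggests a visit difference in within-session change for a 20-ft walk or a functional reach, and for the SART, where it is most plausible, no figure can be computed. All of that stands, and it is why the gain is called modest.

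The planning argument is also limited. An SD on 58 df has a relative standard error of 1/√(2 × 58) = 9.3%, so inflation of 1 to 5% is well inside sampling error. Only reach at 0.3σ exceeds one standard error. An order-adjusted SD could also be computed later. However, inflation from π is systematic and sampling error is not, and removing it costs almost nothing.

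The plan also offers α = 0.25 as a pilot criterion. There, at 0.38 and 0.32, the losses are smaller: about 0.4, 1.2 and 2.7 points (walking) and 0.4, 1.8 and 3.9 points (reach). The raised type I error needs both a sizeable π and unequal order. Averaged over random allocations it stays near 5%.

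It can be said that the t-test is only shorthand for a fuller mixed model. But the sentence names a specific test as the equivalent of the primary analysis, and the mixed-model description names no visit term either.

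Finally, an order term cannot tell a visit effect from carry-over between visits that may be only 48 hours apart, and carry-over that differed by HIV status would remain in the HIV contrast. That is a limit of the remedy, but the t-test does no better.

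**Conclusion.** The concern holds as a recommended improvement. The primary test leaves out a factor that the design controls, and nothing elsewhere in the plan puts it back. If π is zero, nothing is gained. For π of 0.1 to 0.2σ the gain is at most about 2 points of power at the plan's effects and at most 3 points at the effects with 80% power. At 0.3σ, a large value, it is 3 to 5 and 5 to 7 points. Protection against a shifted contrast matters only if order turns out unequal between the HIV groups.

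These figures assume normal data, the plan's variances, independent changes at the two visits, 30 evaluable women per group and, except where stated, the same π in both HIV groups. The gain for the SART is unknown. Whether order is balanced within HIV group, and whether the mixed models will include visit, are points to clarify and not errors.

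**What to change.** For the primary outcomes, replace the two-sample t-test with a linear regression of each woman's difference in differences on HIV status and order (active first or inactive first), with 57 residual df. This removes the inflation and the shift in full only if π is the same in both HIV groups. If that is doubted, add HIV-by-order with order coded ±1/2 (56 df), so that the HIV coefficient is the average over the two orders. Choose between the two models in writing before unblinding. Neither removes woman-to-woman variation in π.

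Include visit as a fixed effect in the mixed models, and state whether order is balanced within HIV+ and within HIV- women.

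With balanced order and π = 0, power at the plan's effects with 58, 57 and 56 df is 90.40, 90.39 and 90.37% (walking) and 89.83, 89.82 and 89.80% (reach). If order were as unequal as 18/12 versus 12/18, the order term would take power from about 80% to 78–79% when π = 0, which is a reason to balance order within each HIV group. No extra participants, visits or procedures are needed.

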STUDY SETTING The WIHS, established in 1994, was a prospective cohort study of HIV disease progression in women from 9 US cities, in which HIV+ and HIV- participants are well-matched by age, race/ethnicity, education, and high-risk sexual and substance use behavior. 86,87 Semi-annual visits included in-depth interviews, physical exam, and collection of blood, oral, gynecologic, and urine specimens. Current visit structure is now annual in MWCCS. Interviews include sociodemographics, medical history (HIV- and non-HIV related), medication use, HAART use and adherence, substance use, and report of falls and fall-related injury, among others. A neurocognitive testing battery is performed every two years. 88,89 MWCCS has a central Data Analysis and Coordination Center (DACC) and an extensive repository of biological specimens. The Cannabis Research Laboratory, Columbia University Medical Center (CUMC), is directed by [name]. Her laboratory has been conducting federally-funded, placebo-controlled human laboratory studies of cannabis administration for the past 20 years, including studies with HIV+ research volunteers. By collaborating with [name], we have the opportunity to directly assess the acute effects of active vs inactive cannabis administration on a range of clinically-relevant outcome measures, thereby dissociating expectancy effects of cannabis from its pharmacological effects.

STUDY PARTICIPANTS.

We will recruit and test 60 women who report cannabis use within the past six months, including 30 HIV+ women and 30 demographically similar HIV- controls from the Bronx and Brooklyn MWCCS sites, and from clinical populations, such as patients receiving care at Einstein/Montefiore Medical Center, other medical facilities, referred by medical providers, or word-of-mouth if eligibility can be confirmed. Median age of Bronx MWCCS participants is 54 years, with 75% between 49 and 59 years. Inclusion Criteria: (1) current cannabis use (within 6 months) based on self-report, (2) able to perform study procedures, including ability to ambulate independently, (3) adequate hearing and vision, (4) for HIV+ women, use of stable HAART for at least 6 months. Participants must be willing to smoke cannabis during both study

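### The headline detectable effects (0.53 for reach, 0.63 for walking time) do not follow from the stated α, β, variances and 60 women, and they are not the active-versus-inactive contrast they are labelled as

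*Combined protocol and SAP*

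**What the plan says.** The power calculations in Section 7 (Data Analysis) rest on "hypothesis testing at a two sided α =0.05 with β =0.2" and state that the study is "powered to detect (active vs. inactive cannabis) effect sizes of at least 0.53 for functional reach and 0.63 for walking time".

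The supporting inputs are "correlations of ρ =0.82 an 0.87 for walking time and functional reach", "which reduces the variances of within subject difference to 0.27"σ² for walking time and 0.195σ² for functional reach. For a pilot threshold of α=0.25 the paragraph adds that "the detectable effect sizes drop to 0.32 for reach and 0.38 for walking time". It gives no new β for that second pair.

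The statistical analysis text just before it defines the outcome for effect size estimation as the mean of the 15 and 60 minute results minus the same visit's baseline, and says that "this analysis reduces to a two way ANOVA or equivalently two sample t-test of differences in differences". Section 2 (Study Participants) gives the groups: "including 30 HIV+ women and 30 demographically similar HIV- controls". Every woman smokes both active and inactive cannabis.

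**The concern.** Two things do not fit. First, the drop from 0.53/0.63 to 0.32/0.38 is too large for a change in α alone, so the two pairs do not appear to share one β. Second, the figures are described as active-versus-inactive effects, but in this crossover that contrast is within-woman and uses all 60 women. The analysis named for effect size estimation compares HIV+ with HIV- women, 30 against 30.

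This is the plan's only power statement, and the paragraph says no comparable normative data exist for the other outcomes. As written, a reader cannot tell what the study can detect for the drug effect and what it can detect for the HIV-by-drug effect. The benefit of relaxing α is also overstated. The timeline in Section 2 foresees a follow-on grant application, into which these figures could be carried.

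**Working it through.** **Inputs.** From Section 7: two-sided α=0.05, β=0.2; ρ=0.87 (reach) and 0.82 (walking time); second threshold α=0.25. From Section 2: 30 HIV+ and 30 HIV- women, each tested under both conditions. Effects are taken in units of σ, the standard deviation of one measurement, because the plan gives its variances in σ².

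**Step 1: the plan's variances.** With a common correlation ρ among the three measurements, the mean of two post-dose values minus baseline has variance V = σ²[(1+ρ)/2 + 1 − 2ρ] = 1.5(1−ρ)σ².
- Reach: 1.5 × 0.13 = 0.195.
- Walking time: 1.5 × 0.18 = 0.27.

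Both match the plan.

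**Step 2: a check that needs no variance.** For a 30 versus 30 t-test (58 df), the detectable effect is a multiple of the standard error that depends only on α and β. By noncentral t, at 80% power the multiple is 2.849 for α=0.05 and 2.000 for α=0.25, a ratio of 2.000/2.849 = 0.70. The variance and any correlation cancel. The printed ratios are 0.32/0.53 = 0.60 and 0.38/0.63 = 0.60. The most favourable rounding gives 0.325/0.525 = 0.619 and 0.385/0.625 = 0.616. For any group size from 5 to 60 the required ratio lies between 0.65 and 0.71. The two pairs therefore cannot both hold at the stated two-sided α values and β=0.2.

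**Step 3: which pair fails.** Let r be the correlation between a woman's change scores at her two visits. The active-minus-inactive change has variance 2V(1−r), and the standard error of the group difference is √[2V(1−r) × 2/30]. The plan does not give r. If the same ρ also holds across visits, r=0, and the variances are 0.39σ² and 0.54σ², with standard errors 0.161σ and 0.190σ.

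| Setting (30 vs 30, r=0) | Reach | Walking time | Printed |
|---|---|---|---|
| α=0.25, β=0.2 | 0.323 | 0.380 | 0.32 / 0.38 |
| α=0.05, β=0.2 | 0.459 | 0.541 | 0.53 / 0.63 |
| α=0.05, β=0.1 | 0.532 | 0.625 | – |
| α=0.05/3, β=0.2 | 0.535 | 0.630 | – |

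The second pair reproduces and the first does not. Power at 0.53 and 0.63 with α=0.05 is 89.8% and 90.4%. For the first pair to hold at β=0.2, r would have to be about −0.33 (reach) and −0.36 (walking time); the second pair needs 0.02 and 0.00.

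**Step 4: the label.** Active versus inactive in 60 paired women has standard error √[2V(1−r)/60] and is a one-sample t-test on 59 df. At α=0.05, β=0.2 and r=0 it detects 0.230σ and 0.270σ. The worst possible case, r=−1, gives 0.325σ and 0.382σ. The printed 0.53 and 0.63 exceed even that bound.

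**Step 5: range over r** (β=0.2, reach / walking time).

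| r | HIV-by-drug, α=0.05 | HIV-by-drug, α=0.25 | Active vs inactive, α=0.05 | Power of HIV-by-drug test at 0.53 / 0.63, α=0.05 |
|---|---|---|---|---|
| 0 | 0.46 / 0.54 | 0.32 / 0.38 | 0.23 / 0.27 | 90% / 90% |
| 0.25 | 0.40 / 0.47 | 0.28 / 0.33 | 0.20 / 0.23 | 96% / 96% |
| 0.5 | 0.32 / 0.38 | 0.23 / 0.27 | 0.16 / 0.19 | above 99% |

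**The case against.** **An adjusted α.** Both pairs could share β=0.2 if the first used α/3. That is not far-fetched, since there are three primary outcomes. It gives 0.535/0.630, borderline for the printed 0.53. But the paragraph states 0.05 and mentions no adjustment. The inconsistency with the stated inputs stands; its origin is open.

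**The choice of r=0.** The ratio shows only that the pairs disagree. Naming the first as the wrong one relies on r near zero. The match for the second pair is also not unique: a single visit's change compared 30 versus 30 at α=0.05 gives 0.325/0.382, as does r=0.5. This is fair, and the assumption must be visible. None of these readings yields 0.53/0.63 at α=0.05 and β=0.2, however. Unstated dropout to about 22 per group would come close, but would move the α=0.25 pair to roughly 0.37–0.38 and 0.43–0.44, and the paragraph says 60 subjects.

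**The label.** The analysis text uses similar words when it describes the interaction, so the parenthesis may only name the score being compared. That makes the label ambiguous rather than plainly false. Since the plan intends to test both the drug effect and the interaction, the contrast needs naming on either reading.

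**Importance.** Section 9 calls this a pilot not fully powered for group differences, the sample size is also argued on estimation grounds, and the error is conservative. All of that is true and limits the consequence. It does not make the printed figures agree with their inputs.

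**Conclusion.** The concern holds. At the stated settings the HIV-by-drug comparison detects 0.46σ (reach) and 0.54σ (walking time), not 0.53 and 0.63, assuming r=0; a positive r lowers these further. The conflict between the two printed pairs (ratio 0.60 against 0.70) does not depend on r or on the variances. The gain from relaxing α is therefore shown as a 40% drop when it is 30% at constant β. The printed figures also cannot be the within-woman active-versus-inactive contrast for any r. That 90% power was used for the first pair fits the numbers but remains an inference. The study can detect somewhat smaller effects than it claims, and the case for 60 women is unaffected. This should be fixed, with high confidence.

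**What to change.** Ask the sponsor which α, β, contrast and between-visit correlation produced each pair, then restate the paragraph so that every figure carries those inputs. Using one β of 0.2 and r=0, it would read:

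- HIV-by-drug difference in differences, 30 versus 30: 0.46σ for reach and 0.54σ for walking time at two-sided α=0.05; 0.32σ and 0.38σ at two-sided α=0.25.
- Active versus inactive, 60 paired women: 0.23σ and 0.27σ at two-sided α=0.05.

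State that r=0 is an assumption and give the range for r=0.25 and 0.5 from the last table above. If the sponsor confirms 90% power for the first pair, 0.53 and 0.63 can stay, with β=0.1 written beside them and the HIV-by-drug contrast named; the comparison with α=0.25 should then say that β differs. If an adjusted α was used, state it.

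The cost is the wording of one paragraph. Design, tests and number of participants do not change.
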